9.2 DATA MANAGEMENT

At the completion of the study, a report will be generated. Data from this study will be referred to only using study number and will be retained by the PI's for a minimum of 25 years on a password-protected server held by the School of Optometry and Vision Science. After 25 years, data will be disposed of in accordance with the guidelines laid out by the University of Waterloo.

10 PROTOCOL TRAINING

Training of the graduate student will be conducted for this study to educate him about the testing procedures.

11 STUDY MONITORING

Study records may be inspected by the investigator's supervisor, the Office of Research Ethics at the University of Waterloo, and by regulatory authorities in Canada (Health Canada); however, no records containing identifiable/personal information will be permitted to leave the School of Optometry and Vision Science, Contact Lens Clinic.

12 STUDY MANAGEMENT

12.1 STATEMENT OF COMPLIANCE

This clinical study is designed to follow the ethical principles in the Declaration of Helsinki, with the ICH guidelines for Good Clinical Practice (GCP), with the University of Waterloo's Guidelines for Research with Human Participants and with the Tri-Council Policy Statement: Ethical Conduct for Research Involving Humans, 2nd Edition.

- Declaration of Helsinki
- ICH E6 - International Conference on Harmonisation; Good Clinical Practice
- <https://uwaterloo.ca/research/office-research-ethics/research-human-participants>
- https://uwaterloo.ca/research/sites/ca.research/files/uploads/files/uw_statement_on_human_research_access_checked.pdf
- <http://www.pre.ethics.gc.ca/eng/policy-politique/initiatives/tcps2-eptc2/Default/>

12.2 ETHICS REVIEW

This protocol will be submitted to the Office of Research Ethics (ORE) at the University of Waterloo and reviewed by a Research Ethics Committee. Notification of ethics clearance of the application is required prior to the commencement of the study.

12.3 ADVERSE EVENTS

12.3.1 ADVERSE EVENT DEFINITIONS

An 'adverse event' refers to any undesirable clinical occurrence in a participant, whether it is device-related or not. Adverse events (AE) may be classified as 'unanticipated adverse device effects,' 'serious adverse events,' 'significant adverse events,' or 'non-significant adverse events,' as defined below.

| Classification | Definition |
|-------------------------------------|---|
| Serious Adverse Event | Those events that are life-threatening, or result in permanent impairment of a body function, or permanent damage to a body structure or necessitate medical (therapeutic) or surgical intervention to preclude permanent impairment of a body function or permanent damage to a body structure. |
| Significant Adverse Event | Those non-serious adverse events that occur with contact lens usage that are not sight-threatening but are usually symptomatic and may warrant therapeutic management and /or temporary or permanent discontinuation of contact lens wear. |
| Non-Significant Adverse Events | Those less severe non-serious adverse events that occur with contact lens usage that are not sight-threatening, may or may not be symptomatic and may warrant palliative management, such as ocular lubricants or temporary interruption of contact lens wear. |
| Unanticipated Adverse Device Effect | Adverse events in a clinical trial that were not previously identified in the protocol in terms of nature, severity, or degree of incidence. An Unanticipated Serious Adverse Device Effect is an unanticipated adverse event that is serious in nature and caused by or associated with the device and is considered reportable. |

AE classification, coding and examples are provided in the following table used for reporting.

| Code | Condition | Reporting |
|-----------------------------------|--|-----------|
| Serious Adverse Events | | |
| 01 | Presumed infectious keratitis or infectious corneal ulcer | |
| 02 | Permanent loss of ≥ 2 lines of best spectacle corrected visual acuity (BSCVA) | |
| 03 | Corneal injury that results in permanent opacification within central cornea (6mm) | |
| 04 | Uveitis or Iritis (e.g. presence of anterior segment inflammation as described in ISO 11980, Annex B) | |
| 05 | Endophthalmitis | |
| 06 | Hyphema | |
| 07 | Hypopyon | |
| 08 | Neovascularization within the central 6mm of cornea | |
| 00 | Other serious event | |
| Significant Adverse Events | | |
| 11 | Peripheral (outside central 6mm), non-progressive, non-infectious ulcer | |
| 12 | Symptomatic corneal infiltrative event | |
| 13 | Superior epithelial arcuate lesions (SEALs) involving epithelial split | |
| 14 | Corneal staining \geq dense coalescent staining up to 2mm in diameter (e.g. moderate, ISO 11980 grade 3) | |
| 15 | Corneal neovascularization \geq 1.0mm vessel penetration (e.g. \geq ISO 111980 Grade 2), if 2 grade change from baseline | |
| 16 | Any temporary loss of ≥ 2 lines BSCVA for ≥ 2 wks | |

| | | |
|--------------------------------|--|--|
| 17 | Any sign and/or symptom for which participant is administered therapeutic treatment or which necessitates discontinuation of lens wear for ≥ 2 weeks | |
| 10 | Other significant event | |
| Non-significant Adverse Events | | |
| 21 | Conjunctivitis (bacterial, viral or allergic) | Notify ORE as soon as possible, within 24 hours; |
| 22 | Papillary conjunctivitis if \geq mild scattered papillae/follicles approximately 1mm in diameter (e.g. ISO 11890 Grade 2), if 2 grade change from baseline | |
| 23 | Asymptomatic corneal infiltrative events | |
| 24 | Any sign and/or symptom for which temporary lens discontinuation for > 1 day is recommended (if not already classified) | |
| 20 | Other sign and/or symptom warranting classification as a non-significant adverse event | |

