4 MATERIALS AND METHODS

4.1 STUDY DESIGN

4.1.1 OVERALL DESIGN

This will be a prospective, dispensing cross over study design involving five visits.

The first visit will involve screening, baseline measurements and trial fitting of scleral lenses. At this visit, participants may be wearing their habitual contact lenses (if any) as prescribed by their Optometrist/Ophthalmologist.

The second visit will be a dispensing visit of one of the pairs of the scleral contact lens designs (with or without Hydra-PEG, randomly assigned) and a single follow up visit after 8-10 hours of lens wear in a day, four weeks later (third visit). A washout period of a minimum of 48 hours will be applied between lens types. The fourth and fifth visits will be for the other scleral contact lens visits (delivery and after 4 weeks).

Scleral contact lenses to be worn in this study will be made of Boston XO material (with and without Hydra PEG) approved by Health Canada for commercial purposes. The scleral contact lenses will have a diameter of 14.8-15.4mm. The manufacturer's recommended guidelines will be used to select and fit these lenses, with an expected corneal clearance between 250 μ m to 350 μ m. As to which of the two scleral contact lenses are being assessed, both the investigator and the participant will be masked as the Optometric assistant will provide the lenses in an unlabelled case.

Masking the investigator will prevent bias when measuring the primary outcome variables and analyzing the data.

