4.5 STUDY PROCEDURES

4.5.1 SCREENING AND BASELINE MEASUREMENTS

Screening & Baseline procedures: Participants will present to the screening visit. The cornea sagittal depth/height will be measured with the Visante OCT. OSDI and SPEED will be collected from the participant. Confirmation and change of dry eye status will be assessed based on tear

osmolarity and MMP-9 measurements using the Tearlab Osmolarity System and InflammaDry® test kits respectively. Additionally, their auto-refraction, visual acuity measurements as well as corneal topography with the Pentacam will be carried out. Eligibility will be confirmed, and a baseline biomicroscopy assessment will be performed to assess corneal. (Visit 0-0).

Ocular Surface Imaging: The eyes of the participants will be examined at the slit-lamp biomicroscope and imaged using the Keratograph® 5M. Participants will be seated at the Keratograph® 5M instrument and asked to blink 2-3 times and hold their eyes open for a few seconds until the instrument software takes a picture of the eye. This image acquisition will be repeated twice. This procedure will also be used to assess corneal and conjunctival staining. (Visits 0-0; 1-1; 2-2).

Fitting of the scleral lenses: Participants will be trial fitted with a scleral lens design using the Pentacam software and following the manufacturer's recommendation, but one pair will be ordered non-coated and the other pair will be Hydra-PEG coated (randomly selected). Acceptable fitting will be based on manufacturer's recommended guidelines for fitting these lenses. All scleral lenses used in the study will be made of Boston XO material. Participants will be instructed on insertion, removal, and proper handling of lenses (Visits 0-0, 1-1 2-1).

Imaging procedure With and Without Test Lenses: The anterior segment of the eye and the lens fit will be imaged and assessed using the Visante OCT, Keratograph 5M, Pentacam and Spectralis OCT prior to lens wear and after the lens delivery appointment (Visits 1-1, 2-1), and at the follow up appointment (Visits 1-2, 2-2).

Corneal Thickness Measurements: Corneal thickness will be measured with the Spectralis OCT and Pentacam before and after lens wear (Visits 0-0, 1-2, 2-2). Participants will be seated at the Spectralis OCT and the Pentacam instruments and to blink 2-3 times then hold their eye open for a few seconds until the instrument software takes a measurement of the corneal thickness. This measurement will be repeated twice.

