Visual Acuity Assessment: At the screening and follow up appointments (after four weeks of each lens wear), visual acuity will be assessed using the standard LogMAR visual acuity chart. (Visits 1-2 & 2-2).

Contact Lens Dry Eyes, Quality of life assessment and Wearing experience: CLDEQ-8 (biweekly), CLIQ (weekly) and wearing habit/experience along with subjective grading scales (daily) will be used to assess ocular symptoms, quality of life and wearing experience of each of the two pairs of lenses following the four weeks wearing schedule (8-10hrs daily wear). (Visits 1-2, 2-2). These questionnaires will be filled by the participants daily, weekly, and biweekly respectively for each of the pairs of lenses for the four-weeks wearing schedule.

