4.5.3 FOLLOW-UP VISIT

Following the four weeks of the contact lens wear, the participant will present at the follow-up visit (visits 1-2, 2-2). The lens will be examined with the slit lamp biomicroscope. This will be

followed by visual acuity and imaging with Spectralis OCT (to assess corneal clearance and cornea thickness).

The investigator will carefully remove the contact lens from the eye and immediately collect the tears from the lens bowl for tear analysis. Levels of protease and cytokines in the tears will be assessed.

Slit lamp biomicroscopy mounted camera will be used to assess the corneal integrity and staining. This will be followed by imaging with the Keratograph 5M (for staining) and Spectralis OCT for corneal thickness measurements.

The questionnaire administered (CLDEQ-8, CLIQ and wearing habit/experience along with subjective grading scales) will be collected and reviewed for completeness.

The above-described procedures will be followed for all the lenses to be used in the study.

Table 2 lists a summary of procedures to be conducted at scheduled visits.

Table 2: Summary of procedures at scheduled visits

| Visit | Procedure | Instrument/ application | Form (Appendix #) |
|---|---|---|---|
| Screening, Baseline visit and Trial Lens Fitting (Visit 0-0) | Informed Consent | - | ICL (2) |
| | Demographics & Med. History | - | Screening Form (3) |
| | Ocular surface disease | Self-Administered Questionnaire | OSDI questionnaire (4) |
| | Evaluation of Eye Dryness | Self-Administered Questionnaire | SPEED questionnaire (5) |
| | Vision assessment | LogMAR chart | Study Visit Form for Scleral Lenses (6) |
| | Osmolarity | Tearlab osmolarity system | Study Visit Form for Scleral Lenses (6) |
| | Level of protease (MMP-9) | InflammaDry | Study Visit Form for Scleral Lenses (6) |
| | Tears from ocular surface | Micropipette tear collection kit | Study Visit Form for Scleral Lenses (6) |
| | Ocular surface imaging | Keratograph 5M (K5M) | Study Visit Form for Scleral Lenses (6) |
| | Sagittal height/corneal topography | Visante, Spectralis and Pentacam | Study Visit Form for Scleral Lenses (6) |
| | Biomicroscopy | Slit-lamp with camera | Biomicroscopy Form (7) |
| | Auto-refraction | Auto-refractor | Study Visit Form for Scleral Lenses (6) |
| TRIAL LENS FITTING | | | |
| Lens fitting and examination | Slit lamp with camera | Study Visit Form for Scleral Lenses (6) | |

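### Two adverse event codes are defined by loss of best spectacle corrected acuity, but no visit specifies that measurement, and follow-up acuity is taken before the lens is removed

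*Combined protocol and SAP*

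**What the plan says.** **The codes (section 12.3.1).** Serious code 02 is a permanent loss of two or more "lines of best spectacle corrected visual acuity (BSCVA". Significant code 16 is "Any temporary loss of ≥ 2 lines BSCVA for ≥ 2 wks". BSCVA is named nowhere else in the protocol body.

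**Screening, Visit 0-0.** Section 4.5.1 says: "Additionally, their auto-refraction, visual acuity measurements as well as corneal topography with the Pentacam will be carried out". It does not say what correction is worn for the acuity, and no subjective refraction is listed. Section 4.1.1 adds that at this visit "participants may be wearing their habitual contact lenses (if any) as prescribed by their Optometrist/Ophthalmologist".

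**Delivery, Visits 1-1 and 2-1.** Sections 4.4.2 and 4.5.2 take acuity with the study lens on. Table 2 also has a combined biomicroscopy and acuity row above the insertion step, with no correction stated.

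**Follow-up, Visits 1-2 and 2-2.** In section 4.5.3 the lens is first examined on the eye, "followed by visual acuity and imaging with Spectralis OCT". Only then does removal come: "The investigator will carefully remove the contact lens from the eye and immediately collect the tears from the lens bowl". The steps after removal are slit lamp, Keratograph and OCT. Table 2 has the same order, with its vision row above the removal heading and none below. The last follow-up row is exit from the study.

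**General acuity paragraph (section 4.5.1).** This refers to screening and follow-up in its text but codes only the follow-up visits: "visual acuity will be assessed using the standard LogMAR visual acuity chart. (Visits 1-2 & 2-2".

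**The concern.** An event defined by a change in a measurement needs that measurement at baseline and again after exposure. Here the schedule provides neither in the form the codes require. A study team that followed the protocol exactly would finish without a defined baseline BSCVA and without any lens-off acuity after the second lens. A final report of no code 02 or code 16 events would then partly reflect that nobody looked.

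The missing baseline matters most. A post-wear reading can be added late, but a BSCVA from before lens wear cannot be recovered once wear has begun.

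**Working it through.** The plan gives no figure to reproduce here, so the check is a count of codes and of scheduled acuity entries.

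**1. Codes that depend on BSCVA.** Leaving out the three catch-all codes (00, 10, 20), section 12.3.1 lists 01 to 08 (8 codes), 11 to 17 (7) and 21 to 24 (4). 8 + 7 + 4 = 19. Codes 02 and 16 are 2 of the 19, and one of them is serious.

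**2. Acuity entries per participant in Table 2.** Lens status is read from each row's position relative to fitting, insertion or removal.

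| Visit | Position in Table 2 | Study or trial lens | Specified as BSCVA |
|---|---|---|---|
| 0-0 | before trial fitting | off (habitual contact lenses not ruled out) | no |
| 0-0 | during trial fitting | on | no |
| 1-1 | before insertion | off, correction unstated | no |
| 1-1 | after insertion | on | no |
| 1-2 | before removal | on | no |
| 2-1 | before insertion | off, correction unstated | no |
| 2-1 | after insertion | on | no |
| 2-2 | before removal | on | no |

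Totals: 3 off + 5 on = 8 entries, of which 0 of 8 are specified as BSCVA.

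**3. Lens-off readings after each wearing period.**
- After lens 1: one, at Visit 2-1, at least 48 hours after Visit 1-2. It rests on Table 2 alone. Section 4.5.2 lists acuity only after insertion, and on that text the count is 0.
- After lens 2: 0, for each of up to 25 participants. Section 4.5.3 and Table 2 agree on this.

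**4. Duration terms.** Code 02 needs permanence and code 16 needs at least two weeks. No visit is scheduled after 2-2, so scheduled data cannot establish either term for a loss that arises with lens 2.

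**5. Can lens-on acuity stand in?** The Introduction describes a lens that vaults the cornea over a fluid reservoir. It is a reasonable inference that acuity through that system can differ from spectacle acuity when the corneal surface has changed. The documents do not state this, and a loss from opacity or inflammation might still show with the lens on. The supportable wording is that a loss could be missed.

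**The case against.** The strongest reply is that the code table is a classification for reporting and not a list of scheduled endpoints. Participants are told to make contact about symptoms, and blurred vision is among those named (section 5). Unscheduled visits are allowed (section 4.4.7). Section 12.3.2 provides for referral to an ophthalmologist and for following each event until it resolves. The cornea is examined with the lens off by slit lamp, Keratograph and OCT at both follow-up visits. Acuity and adverse events are recorded on Appendices 6 and 13, which are listed but not reproduced and may state the correction.

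Most of this stands, and it limits the point to losses that cause no complaint and leave no visible sign. It does not remove the point. None of these routes specifies BSCVA, follow-up to resolution begins only once an event is recognised, and none supplies a defined baseline. The forms might state a correction, but section 4.5.3 and Table 2 both omit a reading after removal.

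Three stronger readings are tempting, and the documents do not support them:
- **That codes 02 and 16 cannot be evaluated at all.** The event-driven routes can still identify a loss that is noticed.
- **That the uneven lens-off readings bias the comparison of coated with uncoated lenses.** Lens order is randomly assigned, so the imbalance is between periods and does not systematically favour one lens. Section 3 does not list BSCVA loss as an outcome, and section 9.1 plans no comparison of adverse events.
- **That one lens-off reading at Visit 2-2 would settle either code.** Through the Visit 0-0 correction it does not show best correction at that time. Soon after 8 to 10 hours of wear it may catch transient blur. Alone it shows neither permanence nor a two-week duration.

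**Conclusion.** The concern holds as a gap in routine safety ascertainment. Two of 19 specific codes, one of them serious, depend on a measurement that the protocol body specifies at 0 of 5 visits. The gap is widest after lens 2, where no lens-off acuity is scheduled. A silent loss of spectacle acuity could pass unseen in scheduled data, with no defined baseline to judge it against.

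This rests on two assumptions: that the row order in Table 2 is the order of testing, which section 4.5.3 supports for the follow-up visits, and that the unreproduced forms do not already define the correction. No primary outcome is affected. The change is still worth making before enrolment because the baseline cannot be obtained later.

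**What to change.** 1. **Section 4.5.1 and Table 2, Visit 0-0:** record acuity per eye as BSCVA, without contact lenses and before trial fitting, with the scheduled auto-refraction as the starting point.
2. **Section 4.5.3 and Table 2, Visits 1-2 and 2-2:** add one lens-off LogMAR acuity per eye after tears have been collected from the lens bowl, so that sampling is not delayed. Treat it as a screen against the Visit 0-0 value.
3. **Section 12.3.1:** state that an apparent loss of two or more lines is confirmed with updated refraction, and with a repeat reading late enough to judge the code's own duration term, before code 02 or 16 is assigned or ruled out. After Visit 2-2 this means a recheck for that participant.
4. **Keep lens-on acuity** as the performance measure.
5. **Reconcile acuity timing** across the acuity paragraph of section 4.5.1 (screening named in the text but missing from the visit codes), section 4.5.2 (after insertion only) and Table 2 (before and after insertion).

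The routine cost is one reading per eye at two visits. With both eyes fitted, that is 2 × 2 = 4 readings per participant, or at most 4 × 25 = 100 across the study. The LogMAR chart and auto-refractor are already in use. The downside is slightly longer follow-up visits and an occasional recheck, some of them prompted by transient blur after removal.

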4.2.2 NUMBER OF PARTICIPANTS

Recruitment: Participants who are patients of the University of Waterloo (UW) contact lens or ocular health clinics and those who are not UW patients but have previously participated in DE studies through CORE will be invited to participate in this study. With the patient's permission, the investigators will initiate recruitment according to the in-person script or flyers approved by the Office of Research Ethics (Appendices 1a-c). The investigators will discuss the project where any questions regarding the study procedures and any risks associated with the study can be answered. Eligibility will be determined using the inclusion and exclusion criteria. Current contact

lens wear of any lens type is not necessary for the DE participants. Informed consent will be obtained for all participants prior to their enrollment in the study (Appendix 2).

INCLUSION CRITERIA

A person is eligible for inclusion in the study if he/she:

- Is at least 18 years of age and has full legal capacity to volunteer.
- Has read, understood, and signed the information consent letter.
- Has been diagnosed with dry eyes.
- Has reduced tear break up time (NITBUT) and/or reduced tear meniscus height (TMH), clinical sign of dry eye disease and contact lens discomfort or is symptomatic of dry eye.
- Is willing and able to follow instructions and maintain the appointment schedule.
- Has greater than 13 points on the OSDI.
- Has greater than 4 points on the Standardized Patient Evaluation of Eye Dryness (SPEED).

EXCLUSION CRITERIA

A person will be excluded from the study if he/she:

- Is using any topical medications that will likely affect the study outcome.
- Has undergone any form of corneal surgery.
- Has any known allergies or sensitivity to the diagnostic pharmaceuticals or products, such as fluorescein, used in this study.
- Has persistent, clinically significant corneal or conjunctival staining using sodium fluorescein dye not related to the signs of dry eye.
- Has any clinically significant lid or conjunctival abnormalities and active neovascularization on the cornea.
- Anatomic variations of the conjunctiva that can impair proper scleral or soft contact lens wear/fitting
- Ocular pathology other than dry eye (e.g. glaucoma, macular degeneration) which may significantly impact visual function and assessment.
- Is participating in any other type of eye related clinical or research study.

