- Has any active ocular infection and may require topical medications.
- Currently taking any systemic medication that may affect the study outcome.
- Is pregnant
- Has been diagnosed, recovered, or tested positive but asymptomatic with COVID-19.

For the purposes of this study, active ocular disease is defined as infection or inflammation which requires therapeutic treatment. Mild (i.e. not considered clinically relevant) lid abnormalities (blepharitis, meibomian gland dysfunction, papillae), corneal and conjunctival staining and dry eye are not considered active ocular disease. Neovascularisation (non-active) and corneal scars are the result of previous hypoxia, infection or inflammation and are therefore not considered as active ocular disease.

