12.3.2.1 REPORTING ADVERSE EVENTS

All potential Serious and Unanticipated Adverse Device Effects that are related or possibly related to participant participation will be reported to the Principal Investigator's supervisor within 24 hours of the investigator becoming aware of the event. The Principal Investigator will report the event to the ORE as soon as possible (by fax, mail/delivery, phone, or email) following the University of Waterloo Office of Research Ethics reporting guidelines. All fatal or life-threatening events will be reported immediately to the ORE.

Significant and Non-Significant Adverse Events will be reported to the ORE within 24 hours.

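### Code 14 sets no baseline condition although dry-eye staining of any grade may enter, so unchanged entry findings can be coded as Significant adverse events; code 08 has a narrower form of the same gap

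*Combined protocol and SAP*

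**What the plan says.** **Entry (section 4.2.2).** The staining exclusion reads: "Has persistent, clinically significant corneal or conjunctival staining using sodium fluorescein dye not related to the signs of dry eye". The vessel exclusion reads: "Has any clinically significant lid or conjunctival abnormalities and active neovascularization on the cornea". The closing paragraph of the criteria adds that "Neovascularisation (non-active) and corneal scars are the result of previous hypoxia, infection or inflammation" and do not count as active ocular disease. A further criterion excludes ocular pathology other than dry eye that could materially affect visual function and its assessment.

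**Event codes (section 12.3.1).** Code 14, in the Significant class, is corneal staining at or above "dense coalescent staining up to 2mm in diameter (e.g. moderate, ISO 11980 grade 3". Code 08, in the Serious class, is "Neovascularization within the central 6mm of cornea". Neither row mentions baseline. Codes 15 (corneal neovascularisation by vessel penetration) and 22 (papillary conjunctivitis) both end with "if 2 grade change from baseline".

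**Reporting (section 12.3.2.1).** "Significant and Non-Significant Adverse Events will be reported to the ORE within 24 hours". Serious events go to the supervisor within 24 hours and then to the ORE as soon as possible, but only if judged at least possibly related to taking part.

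**Forms (section 12.3.2).** One Adverse Event Form is completed per adverse event, separately for each eye, and the participant is followed until the event resolves.

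**The concern.** This is a dry-eye trial, and corneal staining is one of the signs of the disease under study. A sign that is allowed at entry is also, above a fixed severity, the definition of a Significant adverse event. Without a baseline condition, the row cannot separate staining that the participant brought to the study from staining that appeared or worsened under a lens.

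At stake is the safety record. Entry disease would be mixed with new findings, an eye that had partly improved could still be coded as an event, and real worsening would be harder to see. The ORE could also receive 24-hour reports about findings that were known at screening.

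**Working it through.** The plan gives no figure to reproduce here, so the check sets the texts side by side.

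| Finding | Allowed at entry? | Event row | Baseline condition in row? |
|---|---|---|---|
| Dry-eye corneal staining, any grade | Yes; only staining not due to dry eye is excluded | Code 14, Significant | No |
| Non-active vessels in the central 6 mm | Yes, unless the visual-function criterion applies | Code 08, Serious | No |
| Corneal vessels by penetration | Yes, if non-active | Code 15, Significant | Yes, 2 grades |
| Papillary changes | Mild lid abnormalities are not treated as active disease | Code 22, Non-significant | Yes, 2 grades |

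1. *Is there a ceiling on dry-eye staining at entry?* The exclusion list contains none. The closing paragraph of section 4.2.2 refers to mild staining, but it does so to define active ocular disease and sets no upper limit in the staining criterion.

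2. *Is a baseline comparison implied for code 14?* Two of the four rows above state one and two do not. Corneal neovascularisation appears in both groups: code 15 is judged against baseline and code 08 is not. The table writes the condition out where it is intended, so its absence from a row reads as an absolute threshold.

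3. *Does another section exempt unchanged entry findings?* No. The only carve-out, section 12.3.1.1, covers transient adaptive symptoms and not slit-lamp signs.

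4. *What follows for code 14?* An eye at or above the threshold at Visit 0-0 that is unchanged at Visit 1-2 or 2-2 meets the row. So does one that has improved but remains at or above it. Section 12.3.2.1 applies no relatedness filter to Significant events, so the 24-hour report follows.

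5. *What follows for code 08?* The row is met by old central vessels, but the 24-hour report to the supervisor applies only to events judged at least possibly related to participation. Old, unchanged vessels would ordinarily not pass that test.

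6. *How many forms?* Section 12.3.2 asks for a form per event and per eye. Treating a persistent finding as one continuing event gives 1 form × 2 eyes = 2 forms at most per affected participant. For k affected participants the ceiling is 2k. The documents do not give k. Purely as an assumption, k = 2 to 5 of the 25 enrolled gives 2 × 2 = 4 to 2 × 5 = 10 forms.

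**The case against.** The best defence is that the definitions above the table govern its rows. Section 12.3.1 describes an adverse event as an occurrence, ties Significant events to lens use, and ties Serious events to a threat to life, permanent harm, or intervention to prevent permanent harm. A stable finding from before the first lens fits these poorly, and an improved one fits worse. An investigator might therefore never code it. This softens the problem but does not remove it: nothing says that unchanged entry findings are exempt, and two assessors could code the same eye differently.

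Other points for the plan stand. The introduction says the interest is in less severe dry eye, so entry at the code 14 level may be uncommon. Capturing too much dense staining or central neovascularisation is a defensible caution. Adverse events are not an outcome variable and have no planned test, and an unchanged entry finding would tend to appear under both lenses.

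A reader might infer three stronger things that the documents do not support:

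- *A form at every lens visit*, that is 4 visits × 2 eyes = 8 per participant. Section 12.3.2 counts events and not visits, and under section 4.5.2 the slit-lamp assessment at Visit 1-1 comes before the dispensed lens is inserted.
- *Old central vessels reported as a matter of course.* The relatedness filter, and the visual-function exclusion that may remove some of these eyes, make this unlikely.
- *Participants lost from the study as a result.* Discontinuation under section 7 for a slit-lamp finding or an adverse event is at the investigator's discretion.

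**Conclusion.** The concern holds for code 14 and, more weakly, for code 08. Eligibility and the event table are inconsistent: applied as written, code 14 can turn permitted entry disease into a reportable Significant event. Only eyes already at or above the dense coalescent level are affected. Milder staining does not meet code 14, and vessels outside the central 6 mm do not meet code 08.

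The size is about one form per affected eye, up to 2 per participant, assuming that a persistent finding is handled as one event. How many participants would enter at that level is unknown. The effect is confined to adverse event classification, counting and reporting; efficacy and sample size are not affected.

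**What to change.** Reconcile section 4.2.2 with the code table in section 12.3.1:

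- Class a code 14 or code 08 finding as an adverse event only when it is new or worsened from the pre-lens Visit 0-0 biomicroscopy.
- Record a finding already present at Visit 0-0 as a baseline condition.
- Count once a worsening that begins in period 1 and persists into period 2. With Visit 0-0 as the fixed reference it would otherwise be counted again.

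The investigators should set how large a change is required; it need not be the 2 grades used in codes 15 and 22. The change concerns classification only, and clinical handling of any finding stays as it is.

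The cost is wording in two table rows plus a sentence on counting. Biomicroscopy is already scheduled at Visit 0-0, but the content of the Biomicroscopy Form (Appendix 7) is not shown, so the form must be checked to confirm that it captures the staining grade and the location of any vessels. The small downside is that the assessor must look up the Visit 0-0 record when classifying a finding.
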